7.2 Clinical Laboratory Evaluations

Observed values and change from baseline in haematology, prothrombin time, international normalisation ratio, biochemistry and urinalysis assessments will be summarised over time. If the test results are reported in categorical format, the results will be summarised by subject counts and percentage for each category.

Each haematology, prothrombin time, international normalisation ratio, biochemistry and urinalysis parameter will be classed as low, normal, high based on the reference ranges. Shift tables in relation to the normal range from baseline over time will be presented.

Haematology including serology, prothrombin time, international normalisation ratio, biochemistry and urinalysis data will be listed separately including change from baseline, reference ranges flagging all out of range values and also flagging any assessments with at least one clinically significant value.

Separate listings of out of range laboratory measurements recorded throughout the study will be provided. Separate listings will also present local laboratory results where these are collected.

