## 7. SELECTION AND WITHDRAWAL OF SUBJECTS

### 7.1 Subject numbers

A total of 16 subjects are planned to be enrolled in the study to receive active IMP. Subjects that withdraw during the [REDACTED] run-in phase, will be replaced. Subjects that withdraw from the study after receiving active IMP, will not be replaced.

Subject eligibility will not be re-assessed [REDACTED] run-in period; the run-in period is for the purposes of analysis.

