### 7.3 Exclusion criteria

Subjects are excluded from the study if any of the following exclusion criteria are met:

1. Non-ambulatory (full time) wheel chair user
2. Receiving stimulant medication
3. Receiving other medications/therapies not stable (changed) within 4 weeks prior to Run-in ([REDACTED])
4. Medical illness or other concern which would cause investigator to conclude subjects will not be able to perform the study procedures or assessments or would confound interpretation of data obtained during assessment
5. Current enrolment in a clinical trial of an investigational drug or enrolment in a clinical trial of an investigational drug in the last 6 months
6. Women of child bearing potential who are pregnant, lactating or not willing to use a protocol-defined acceptable\* contraception method if sexually active and not surgically sterile
7. Men, if engaged in sexual relations with a female of child-bearing potential, not using an acceptable\* contraceptive method if not surgically sterile
8. Gastrointestinal disease which may interfere with the absorption, distribution, metabolism or excretion of the study medication and impact the interpretability of the study results
9. Current clinically significant (as determined by the investigator) cardiovascular, renal, hepatic, endocrine or respiratory disease
10. Clinically significant heart disease (in the opinion of the investigator) or second or third degree heart block, atrial flutter, atrial fibrillation, ventricular arrhythmias, or is receiving medication for treatment of a cardiac arrhythmia
11. Average QTcF value of >450msec at [REDACTED]
12. Kidney disease requiring ongoing treatment
13. A history of chronic liver disease with current out of range value for ALT, clinically relevant hepatic steatosis or other clinical manifestations of ongoing liver disease
14. Current ALT value > 2X the upper limit of the normal reference range at [REDACTED] ([REDACTED]) (may repeat to confirm)

15. Current total bilirubin value greater than the upper limit of the normal reference range at [REDACTED] (unless due to Gilbert's syndrome) (may repeat to confirm)
16. HbA1c values greater than 6% or 42.0mmol/mol at [REDACTED] (may repeat to confirm)
17. TSH values outside of the normal reference range at [REDACTED] (may repeat to confirm)
18. Serum creatinine >150 µmol/L and creatinine clearance ≤ 60 mL/m (according to Cockcroft-Gault formula) at [REDACTED] (may repeat to confirm)

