#### **10.4.7 Abuse, Misuse, Overdose or Medication Error**

Subjects should not exceed the maximum daily doses or take any two doses within an 8 hour interval. There is no specific antidote to tideglusib. In the event of an overdose, appropriate supportive measures should be employed as clinically indicated and the Medical Monitor must be informed immediately. The investigator should determine appropriate supportive assessments which may include a thorough assessment for potential hepatotoxicity, including assessment of serum chemistries, with particular attention to ALT and bilirubin levels, after the cessation of drug. Repeat examinations should be conducted as clinically indicated.

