1 INTRODUCTION

This document details the statistical analysis of the data that will be performed for the AMO Pharma Ltd study: A Single-Blind, Phase 2 Study to Evaluate the Safety and Efficacy of Tideglusib 400mg or 1000mg for the Treatment of Adolescent and Adult Congenital and Juvenile-Onset Myotonic Dystrophy.

The proposed analysis is based on the contents of protocol version 4.0 (dated 09-JAN-2017). In the event of future amendments to the protocol, this statistical analysis plan (SAP) may be modified to account for changes relevant to the statistical analysis.

The table, listing and figure shells are supplied in a separate document.

The analysis and statistics reporting will be conducted at [REDACTED] using SAS version 9.2 or higher.

Summary statistics will consist of number of subjects(n), mean, standard deviation (SD), minimum, median and maximum, unless specified otherwise. The precision of these variables is defined in the table, figure and listing shells document.

For categorical variables, the number and percentage of subjects in each category will be presented, based on the number of non-missing observations apart from disposition of subjects, protocol deviations, background and demographic characteristics, prior and concomitant medications and adverse events where the percentage will be based on the number of subjects in the analysis set.

Where mentioned in this SAP, "active treatment" will relate to tideglusib treatment.

Unless otherwise stated, baseline is defined as the last non-missing value (including scheduled and unscheduled assessments) prior to the subject receiving active treatment.

In the final analysis of the combined Cohort 1 and Cohort 2 subject data, data will be summarised in tabular form by the intended dose group according to the cohort (Tideglusib 400mg and Tideglusib 1000mg) apart from disposition of subjects, protocol deviations, and background and demographic data which will be summarised by dose group and overall subjects. In the analysis to be conducted at completion of Cohort 1, the data will be summarised in tabular form for the Tideglusib 1000mg dose group only.

Listings will be sorted by dose group, subject number and time of assessment.

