7 SAFETY EVALUATION

7.1 Adverse Events

Adverse events will be coded using the latest MedDRA dictionary version.

A NTEAE is defined as an AE that started on or after the administration of placebo treatment but before the start of the administration of active treatment.

A TEAE is defined as an AE that started on or after the start of the administration of active treatment. If adverse event dates are incomplete and it is not clear whether the adverse event was treatment-emergent, it will be assumed to be treatment-emergent.

A "treatment period" TEAE is defined as an AE that started on or after the start of active treatment but before 2 days after active treatment was discontinued. A "post treatment period" TEAE is defined as an adverse event that started from 2 days after the active treatment was discontinued.

Adverse events of special interest (AESIs) are recorded if it is identified from a review of the haematology and biochemistry results that the subject has clinically significant liver function test elevation.

The following summaries of the total number of “treatment period” TEAEs, “post treatment period” TEAEs and all TEAEs (both “treatment period” and “post treatment period” TEAEs) will be provided at the event and subject levels as indicated:

- TEAEs (events and subjects).
- TEAEs by relationship to active treatment (events and subjects).
- TEAEs by severity (mild/moderate/severe) (events and subjects).
- Serious TEAEs (events and subjects).
- Serious active treatment related TEAEs (events and subjects).
- TEAEs leading to withdrawal (subjects only).
- TEAEs leading to discontinuation of active treatment (subjects only).
- Active treatment related TEAEs leading to discontinuation of active treatment (subjects only).
- TEAEs leading to death (subjects only).

The following summaries of NTEAEs will be provided at the event and subject levels as indicated:

- NTEAEs (events and subjects).
- NTEAEs by severity (mild/moderate/severe) (events and subjects).
- Serious NTEAEs (events and subjects).
- NTEAEs leading to withdrawal (subjects only).
- NTEAEs leading to death (subjects only).

In the above summaries, if a subject experienced more than one NTEAE/TEAE, the subject will be counted once using the most related event for the “by relationship to active treatment” summary and at the worst severity for the “by severity” summary.

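### SAP 7.2 tabulates laboratory results only as low/normal/high, so no visible table counts subjects by the size of an ALT rise, and a subject already above ULN at baseline cannot show an upward shift

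*SAP*

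**What the plan says.** **Entry.** Exclusion 14 (Protocol 7.3) removes subjects with "Current ALT value > 2X the upper limit of the normal reference range at" a visit whose name is blacked out. Exclusion 13 is stricter, but only for subjects with "A history of chronic liver disease with current out of range value for ALT" or other signs of ongoing liver disease. Exclusion 15 removes total bilirubin above ULN unless it is due to Gilbert's syndrome. No AST limit is visible.

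**Baseline.** Protocol 7.1 states, with a redaction before the mention of the run-in, "Subject eligibility will not be re-assessed". In SAP section 1, "baseline is defined as the last non-missing value (including scheduled and unscheduled assessments) prior to the subject receiving active treatment".

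**Laboratory displays.** SAP 7.2 says that each "biochemistry and urinalysis parameter will be classed as low, normal, high based on the reference ranges", and then: "Shift tables in relation to the normal range from baseline over time will be presented". The same section plans by-visit summaries of observed values and changes from baseline. Under SAP section 1 these give n, mean, SD, minimum, median and maximum. SAP 7.2 also plans listings flagged for out-of-range and clinically significant results, and separate listings of out-of-range values.

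**Liver events.** SAP 7.1 states: "Adverse events of special interest (AESIs) are recorded if it is identified from a review of the haematology and biochemistry results" that liver function tests have risen to a degree judged clinically significant. These events carry a flag in the adverse event listing. They are not named in the list of summary rows.

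**The concern.** The primary endpoint (Protocol 8.1) includes how often objective assessments, laboratory values among them, are abnormal. The liver is the organ the visible text singles out. It has its own entry limits, it is the sole subject of the adverse events of special interest, and the overdose section (Protocol 10.4.7) asks for a hepatotoxicity work-up "with particular attention to ALT and bilirubin levels".

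For liver tests the size of the rise matters as much as whether a limit was crossed. The one categorical display of numeric laboratory results discards size. It also cannot move upward for a subject who starts above ULN. A reader who relied on the shift table would see such a subject as unchanged.

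**Working it through.** The plan gives no figure to reproduce: there is no formal sample size calculation and no expected frequency of raised ALT. The check applies the SAP rule to ALT expressed in multiples of ULN.

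**Inputs.** Eligible under exclusion 14: ALT ≤ 2. Class: high if ALT > 1, otherwise normal (low plays no part here). Group size: 8 (SAP 2.4). The baseline and post-baseline values below are illustrative.

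**Step 1: the shift table.**

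| Baseline (xULN) | Eligible under exclusion 14 | Post-baseline 1.5, 3, 5, 8 or 10 xULN |
|---|---|---|
| 0.8 | yes | normal to high, every value |
| 1.0 | yes | normal to high, every value |
| 1.01 | yes | high to high, every value |
| 1.5 | yes | high to high, every value |
| 2.0 | yes | high to high, every value |

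Above ULN at baseline, no rise registers. At or below ULN, all rises past 1x look alike.

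**Step 2: the other planned summaries.** Take eight subjects, seven unchanged at 0.8 and one rising from 2.0 to p. Mean change = (p − 2)/8, maximum change = p − 2, median change = 0.

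| p | Mean change | Median change | Maximum change | Maximum observed |
|---|---|---|---|---|
| 3 | 0.125 | 0 | 1 | 3 |
| 5 | 0.375 | 0 | 3 | 5 |
| 8 | 0.75 | 0 | 6 | 8 |
| 10 | 1.0 | 0 | 8 | 10 |

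The mean and median dilute the event; the maximum shows it. But the maximum does not say how many subjects rose. If a second subject went from 2 to 5 beside one going from 2 to 8, the maximum observed value would still be 8.

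**Step 3: the same subject with graded classes.** With illustrative classes (≤1, >1–2, >2–3, >3–5, >5–8, >8; assumed, not from the documents), a subject at 2.0 who reaches 3, 5, 8 or 10 moves from >1–2 to >2–3, >3–5, >5–8 or >8. Under the SAP rule all four are high to high.

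**Step 4: comparison within the SAP.** Section 7.3 counts subjects whose systolic pressure, diastolic pressure or heart rate changes by more than 40 mmHg, 20 mmHg or 30 bpm. Section 7.4 counts QT, QTcF and QTcB above 450, 480 and 500 msec and changes beyond 30 and 60 msec. Both count by visit and at any time after baseline. Section 7.2 has neither size thresholds nor a worst-value summary.

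**Step 5: how many subjects.** If k of 8 in a cohort have baseline ALT above ULN, the share that cannot shift upward is k/8: 0% for k = 0, 25% for k = 2, 50% for k = 4. The documents do not give k.

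**The case against.** A reader might infer that the SAP would miss a large ALT rise. The documents do not support that. A rise from 1.9 to 8xULN would appear as the maximum observed value and as a change of 8 − 1.9 = 6.1xULN. The listings show each subject's values with change from baseline and flags, and eight subjects per group can be read line by line. Protocol 10.4.6 requires clinically significant laboratory abnormalities to be recorded as adverse events. A liver event of special interest starting on active treatment would therefore be counted in the TEAE tables by preferred term, severity and relationship; only a separate row is absent. This part of the objection stands.

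It also stands that the primary endpoint speaks of incidence, not grade, and that Protocol 11.4 promises shift tables without ULN multiples. Exclusions 9 and 13 narrow entry with raised ALT. For bilirubin, exclusion 15 largely removes the raised-baseline problem. The laboratory alert and stopping limits in Protocol 9.6 are blacked out and the table shells are a separate document, so a ULN-based display there cannot be ruled out.

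What the objection does not supply is a count. The AE severity scale (Protocol 10.4.2) grades awareness, discomfort and interference with activities, so it does not record the size of an enzyme rise without symptoms. Recording as an event of special interest rests on a judgement for which no numeric threshold is visible. SAP 7.2 does not say whether unscheduled post-baseline results enter the by-visit summaries, and results from local laboratories are only listed.

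**Conclusion.** The point holds for the shift table and for the absence of a count by size, and no further. With baseline ALT above ULN, an upward shift is impossible; with normal baseline ALT, a trivial and a large rise share a cell. The second limitation does not depend on how many subjects enter with raised values.

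Two stronger readings should be avoided. The first is that the primary safety analysis fails for the liver: the maxima, flagged listings and TEAE tables would show a large rise. The second is that a known share of subjects is affected: 0 to 4 of 8 is an assumption, and at zero the raised-baseline problem disappears. The conclusion also assumes that neither the redacted text nor the table shells already contain a ULN-based display. This is a cheap improvement, not a defect that threatens the study's conclusions.

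**What to change.** In SAP 7.2, add one table by dose showing each subject's worst post-baseline ALT and AST, unscheduled values included, in multiples of ULN against baseline category. Include bilirubin for loss of magnitude only. As display cut-points use the 2xULN ALT entry limit and any limits already set in Protocol 9.6, which are redacted here and could not be verified. These are display categories and change no clinical rule. For subjects above ULN at baseline, also show the worst value as a multiple of their own baseline; in the example above, 8/1.9 ≈ 4.2.

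In SAP 7.1, add a row for adverse events of special interest (events and subjects) to the TEAE summary.

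The cost is SAP wording, one descriptive table and one row, all from data already collected. The drawback is another table with small counts, to be read descriptively.

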## 8. STUDY DESIGN

### 8.1 Primary endpoints

Incidence of adverse events (AE), including Serious adverse events (SAE). AEs will be evaluated between baseline and Follow-up Visit, while SAEs will be evaluated between screening and the last clinic visit or until resolution, whenever possible.

The incidence of abnormal findings in objective assessments (e.g. laboratory values, ECGs, and vital signs) during the course of the study will also be assessed.

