### **Laboratory Alerts for Stopping Rules**

The laboratory will inform immediately (within 24 hours after obtaining the result) the investigator or designee and medical monitor if the following laboratory values are observed for a subject:

- [REDACTED]
- [REDACTED]
- [REDACTED]

Depending on the laboratory value(s) for the subject, there are 3 possible actions; the subject will be withdrawn from the study, the dose of their study medication will be reduced or the subject/caregiver will be contacted by the investigator for further evaluation:

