#### **ii. Dose Adjustment (Only applicable for subjects on 1000mg Tideglusib)**

[REDACTED]  
[REDACTED]  
[REDACTED] conduct a brief physical examination, collect vital signs and check for any AEs or changes to concomitant medication. As the study is single-blind to the subject/caregiver on whether they are receiving placebo or active medication rather than dose strength, the subject/caregiver will be instructed to bring both cartons of dispensed medication with them to the unscheduled visit. The carton containing the [REDACTED] sachets will be collected from the subject/caregiver and they will be instructed to re-start taking the [REDACTED] sachets. There will be no adjustment of clinic visits from the originally scheduled appointment.

- This procedure should not take more than 5 days from the time that the investigator is informed of the increased laboratory value, to the time the subject stops medication and starts taking the lower dose of medication
- [REDACTED]  
[REDACTED] (see withdraw from study above)

[REDACTED] to the treatment group where they have been most of the time during the study.

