**iii. Subject/Caregiver contacted by Investigator for further evaluation**

[REDACTED]  
[REDACTED]  
[REDACTED]  
[REDACTED] If yes, the subject should be immediately discontinued from the study (see withdraw from study above). If no, the subject/caregiver should be instructed to call the investigator immediately if they experience any of these symptoms before the next scheduled clinic visit. In addition, the subject should attend clinic within 5 days to allow for collection of clinical labs ([REDACTED], [REDACTED], [REDACTED]), conduct of a brief physical examination, collection of vital signs and check for any AEs or changes to concomitant medication.

[REDACTED]  
[REDACTED]  
[REDACTED]  
[REDACTED]  
[REDACTED]

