**9.7 Treatment Accountability and Compliance Checks**

In accordance with regulatory requirements, the Investigator or designated site staff must document the amount of IMP dispensed and/or administered to study subjects, the amount returned by study subjects, and the amount received from and returned to the Sponsor (or representative) when applicable. Product accountability records must be maintained throughout the course of the study.

Every effort should be made to collect cartons and unused sachets of IMP from the subjects at each visit to allow for accountability and for compliance to be checked. It is essential that subjects and caregivers are given information not to use medication from the previous visit if they do not return all medication. This is to maintain the single-blind and therefore should have equal importance at each visit.

At each visit, the subject diary will be reviewed and compared to the accountability evidence to further ascertain compliance and ensure dose times are recorded for PK sample visits (Week [REDACTED] and Week [REDACTED])

[REDACTED] of IMP from 1000mg to 400mg, the number of sachets for both [REDACTED] or placebo and [REDACTED] or placebo should be counted and documented in medical notes before returning the [REDACTED] sachets to the subject and caregiver.

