#### **10.4.6 Clinical Laboratory Evaluations**

Abnormal laboratory findings (e.g. haematology, liver function, biochemistry, urinalysis) or other abnormal assessments (e.g. ECGs, vital signs) that are judged by the Investigator as clinically significant will be recorded as AEs or SAEs if they meet the definition of an AE, as defined in Section 10.4.1

Clinically significant abnormal laboratory findings or other abnormal assessments that are detected during the study and significantly worsen following the start of the study will be reported as AEs or SAEs.

The Investigator will exercise his or her medical and scientific judgment in deciding whether an abnormal laboratory finding or other abnormal assessment is clinically significant.

Subjects with any TEAE laboratory abnormality (especially LFT abnormalities) will be followed up until recovery or stabilisation of the condition.

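### SAP 7.2 tabulates laboratory data only by visit, so the incidence of abnormal laboratory findings over the study, part of the primary endpoint, has no planned summary figure

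*SAP*

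**What the plan says.** - **Endpoint.** Besides adverse events, Protocol 8.1 says that "The incidence of abnormal findings in objective assessments (e.g. laboratory values, ECGs, and vital signs) during the course of the study" will be assessed as part of the primary endpoint.
- **Laboratory tables.** SAP 7.2 summarises observed values and changes over time and adds: "Shift tables in relation to the normal range from baseline over time will be presented". Out-of-range measurements over the whole study are listed, not tabulated.
- **Other objective assessments.** SAP 7.3 (blood pressure, heart rate) and SAP 7.4 (QT intervals) count subjects or outliers beyond stated thresholds both by visit and at any time after baseline. SAP 7.2 has no such sentence.
- **Route to the AE tables.** Under Protocol 10.4.6, abnormal findings "that are judged by the Investigator as clinically significant will be recorded as AEs or SAEs" if they meet the AE definition.
- **Declared changes.** SAP 2.5 names one departure from the protocol analyses, about a biomarker, and no other.
- **Dose reduction.** After a laboratory alert, one of three actions in Protocol 9.6 is that "the dose of their study medication will be reduced". It applies to 1000 mg subjects only, and Protocol 9.7 describes a change "of IMP from 1000mg to 400mg". Protocol 9.6 ii adds: "There will be no adjustment of clinic visits from the originally scheduled appointment". In Protocol 9.6 iii, "the subject should attend clinic within 5 days to allow for collection of clinical labs".
- **Grouping.** SAP section 1 says that in the final analysis "data will be summarised in tabular form by the intended dose group according to the cohort". Protocol 11.4 describes safety changes by treatment dose. A partly redacted sentence closing Protocol 9.6 ii refers to the group in which a subject spent most of the study.

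**The concern.** An incidence over the study is a count of distinct subjects. A set of by-visit tables is not: the same subject may be abnormal at every visit, or a different subject at each. Following SAP 7.2 to the letter produces tables from which this part of the primary endpoint cannot be read. Safety is the primary objective and there are eight subjects per dose, so a difference of a few subjects changes how the result reads.

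Two features add to this:

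- Samples taken at extra visits after an alert fall outside the visit schedule. SAP section 1 uses unscheduled values to define baseline, but SAP 7.2 does not say whether unscheduled post-baseline values enter any table. The most extreme values could therefore be missing from the visit rows.
- If a Cohort 1 subject is reduced to 400 mg and is still tabulated under the intended dose, that subject's later scheduled samples sit in the 1000 mg rows without any mark.

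**Working it through.** The documents give no expected incidence, power or number of dose reductions, so there is no plan figure to reproduce. The steps below compare the texts and then bound what by-visit rows can show.

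**Inputs**

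- n = 8 per dose group (SAP 2.4).
- Biochemistry and haematology at every visit (Protocol 10.1.7).
- After baseline, the Protocol Table 1 header shows five interim visits, EOT and follow-up. That is six on-treatment rows, or seven with follow-up. SAP Table 1 appears to show nine visits against ten columns in the protocol. Both tables are damaged in the public copy, so five on-treatment rows is also tried.
- Assumed for illustration: all eight subjects are sampled at each visit, and one is out of range in each row.

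**Step 1: what each source supplies**

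| Source | Distinct subjects over the whole study? |
|---|---|
| SAP 7.2 summaries and shifts | No, by visit only |
| SAP 7.2 out-of-range listings | Not tabulated; can be counted by hand |
| SAP 7.1 AE tables | Yes, but only for abnormalities judged clinically significant |
| SAP 7.3 and 7.4 | Yes, for set thresholds in vital signs and QT only |

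**Step 2: bounds from by-visit rows**

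With counts a₁ to a_V in V rows, the number of subjects ever abnormal lies between max(a_v) and min(n, Σa_v). With every a_v = 1 this is 1 to min(8, V).

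| Rows V | Lowest | Highest |
|---|---|---|
| 2 | 1/8 = 12.5% | 2/8 = 25.0% |
| 5 | 1/8 = 12.5% | 5/8 = 62.5% |
| 6 | 1/8 = 12.5% | 6/8 = 75.0% |
| 7 | 1/8 = 12.5% | 7/8 = 87.5% |

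Exact (Clopper-Pearson) 95% intervals are 0.3% to 52.7% for 1/8 and 34.9% to 96.8% for 6/8. The gap between the ends of the range does not depend on any dose being reduced.

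**Step 3: chance flags in an ever-abnormal count**

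Assume that reference ranges cover 95% of values and that six samples are independent. The probability of at least one out-of-range value is 1 − 0.95⁶ = 1 − 0.735 = 0.265, about 26% per parameter, or 8 × 0.265 ≈ 2.1 of eight subjects. Positive correlation between a subject's samples lowers this.

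**Step 4: mixing of doses, if reductions occur**

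Suppose r Cohort 1 subjects are reduced, remain on treatment and are tabulated by intended dose. The share of a full later 1000 mg row sampled on 400 mg is r/8: 0% for r = 0, 12.5% for r = 1, 25.0% for r = 2 and 37.5% for r = 3.

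**The case against.** The strongest reply is that little is lost:

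- With eight subjects per dose, anyone can count names in the listings of subjects with out-of-range values.
- Abnormalities that matter clinically become AEs and are counted once per subject and preferred term. Clinically significant liver-test elevations are also flagged as events of special interest.
- Protocol 11.4 itself plans change summaries and shift tables at chosen time points, and Protocol 8.1 prescribes no particular table.
- The shells are a separate document and may contain a whole-study row.
- SAP 7.3 and 7.4 are not exact precedents. They count threshold exceedances, whereas a count of any low or high value is broader, picks up chance flags and includes subjects already abnormal at baseline.

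Most of this stands as a limit on the harm. It does not supply the figure. A hand count from a listing is not a planned summary of a primary endpoint component, the AE route narrows abnormal to clinically significant, and the SAP text does not ask the shells for such a row. The chance-flag point is fair and belongs in the fix.

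Two stronger readings are tempting:

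- *Later 1000 mg rows do contain 400 mg samples and so look cleaner than 1000 mg was.* The documents do not support this as a statement of fact. It needs a reduction to occur, and none is predicted. It also depends on the grouping, on which the three statements quoted or described above do not agree. If the redacted sentence moves reduced subjects to the group where they spent most time, mixing could run either way.
- *The AE overview hides subjects who could not stay on 1000 mg.* It has no row for dose reduction. But SAP 4.4 summarises exposure separately for a partly redacted Cohort 1 subgroup and gives a partly redacted subject count. Together these probably show how many were reduced, and down titration is listed.

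**Conclusion.** The point holds for the laboratory count. Protocol 8.1 puts the incidence of abnormal laboratory findings in the primary endpoint, SAP 7.2 plans only by-visit tables, and SAP 2.5 declares no change that would explain it. On the illustrative assumption of 1/8 in each of six rows, the planned tables cannot tell 12.5% of subjects from 75.0%; with five rows the upper end is 62.5%. This rests on the SAP text alone, since the shells were not seen. It is a missing planned summary, not missing data.

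The dose-mixing part holds only conditionally: if a Cohort 1 subject is reduced, later 1000 mg rows can include 400 mg samples, by one eighth of a full row per such subject under intended-dose grouping. Nothing here bears on which dose or reduction rule is right.

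**What to change.** 1. In SAP 7.2 add, per laboratory parameter and dose group:
   - a shift from baseline category to the lowest and to the highest post-baseline value;
   - the number and percentage of subjects with a low or high value at any time after baseline, with subjects in range at baseline shown separately.
2. State that both use scheduled and unscheduled samples.
3. Add a footnote that repeated sampling will flag some subjects by chance.
4. Reconcile the grouping statements in Protocol 9.6 ii, Protocol 11.4 and SAP section 1. In each visit row, footnote how many subjects were on the reduced dose when sampled.
5. Optional: an AE overview row for dose reduction. SAP 4.4 probably already counts the reduced subjects.

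The cost is a short addition to SAP 7.2, a clarification on grouping, and the matching shells. The out-of-range values, down-titration records and diary dates are already collected and listed, and every planned by-visit table stays. The one drawback is the chance flags, which the in-range-at-baseline split and the footnote keep in view.
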